## 16.1.9 Documentation of Statistical Methods

Receptos, Inc.  
Protocol RPC01-201

Statistical Analysis Plan – Part A, V1.2  
Date Issued: May 20, 2014

- number of relapses in the past 12 months ( $< 2, \geq 2$ ) for ARR endpoint only
- regions (North America, Western Europe, and Eastern Europe)

### 5.1 Sample Size

The primary analysis of Part A will compare the cumulative number of new GdE lesions at the end of Week 24 in each of the RPC1063 groups to the placebo group using a 2-sided Wilcoxon-Mann-Whitney test. For this type of nonparametric analysis, the parameter of interest for sample size/power considerations is the probability that a randomly selected patient in an active treatment arm will have fewer lesions than a randomly selected patient in the placebo arm. Limited data are available from which to estimate this parameter. Based on the use of patient-level data from Tubridy et al. (1999) and Miller et al. (2003), estimates of this probability range from 0.634 to 0.754. Using the approach of Noether (1987), a sample size of 59 patients per group will provide 80% power to detect a difference if the true value of this probability is equal to 0.65 (Noether, 1987). Assuming a dropout rate of 15%, the planned enrollment is 210 patients (70 patients per arm).

### 5.2 Randomization, Stratification, and Blinding

In Part A, patients will be randomized 1:1:1 to receive placebo, RPC1063 0.5 mg, or RPC1063 1 mg. The randomization will be stratified by country. Patients who complete the 24 weeks placebo-controlled treatment period will have the option of entering a 24-week blinded extension period (Weeks 25 to 48). Patients assigned to either RPC1063 treatment group during the double-blind placebo-controlled period will continue in their respective treatment groups during the blinded extension; patients assigned to the placebo treatment group will be randomly assigned in a 1:1 fashion to one of the two RPC1063 treatment groups for the blinded extension.

The randomization will be based on a stratified blocked algorithm and will be done centrally by using Interactive Voice Response System (IVRS).

A “dual assessor” approach will be used to evaluate efficacy and safety to prevent potential unblinding as result of observed efficacy, adverse events (AEs), or laboratory changes. Separate treating and examining investigators will be designated at each center prior to randomization. Patients will be instructed to not disclose symptoms related to their treatment regimen to the blinded evaluator (examining investigator). The blinded evaluator should communicate with patients only as needed to complete the neurological examinations.

In the event that the blinding needs to be broken because of a medical emergency, the Medical Monitor should be contacted immediately. The treatment assignment will be unblinded through an IVRS. Reasons for treatment unblinding must be clearly explained

## 16.1.9 Documentation of Statistical Methods

Receptos, Inc.  
Protocol RPC01-201

Statistical Analysis Plan – Part A, V1.2  
Date Issued: May 20, 2014

and justified in the eCRF. The date on which the code was broken together with the identity of the person responsible must also be documented.

### 5.3 Analysis Populations

#### 5.3.1 Intent-to-Treat (ITT) Population

The ITT population will include all randomized subjects who are confirmed to have received at least one dose of study drug. This will be the primary population for the analysis of efficacy endpoints. All patients in the ITT sample will be analyzed according to the treatment they were randomized to receive and not according to what they actually received, if different.

#### 5.3.2 Per Protocol (PP) Population

The PP population will be a subset from the ITT population without any major protocol deviations. Major protocol deviations will include one or more of the following categories: major inclusion/exclusion criteria violations, poor study drug non-compliance, and other. The prespecified criteria for exclusion from the per protocol population are listed below, and will be finalized in a blinded review prior to the database lock.

- Violation of any of the following three inclusion criteria related to MS specific disease activity:
  - Must have a confirmed diagnosis of MS by the revised 2010 McDonald criteria
  - Must have a baseline EDSS score between 0 and 5.0
  - Must have at least 1 documented relapse within the last 12 months prior to screening, OR, if at least 1 documented relapse occurred within the last 24 months prior to screening, evidence of at least 1 GdE lesion on brain MRI within the last 12 months prior to randomization
- Poor study drug compliance: compliance up to last dose of study drug <80%

#### 5.3.3 Safety Population

The Safety population will include all subjects who have received at least one dose of study drug. All enrolled subjects will be assumed to have taken study drug unless otherwise confirmed. If it is confirmed that a patient never took a dose of study drug, then the patient will be excluded from all safety analysis. All subjects in the Safety population will be analyzed according to the highest dose of RPC1063 treatment actually received and not according to the treatment they are randomized to receive, in the event there is a discrepancy.

## 16.1.9 Documentation of Statistical Methods

Receptos, Inc.  
Protocol RPC01-201

Statistical Analysis Plan – Part A, V1.2  
Date Issued: May 20, 2014

### 5.4 Other Important Considerations

#### 5.4.1 Analysis of Baseline Data and Exposure to Study Drug

All baseline data will be summarized for the ITT population. Baseline data are defined as data collected which are prior to and/or on the date of first dose, usually also the same day as the Week 0 Day 1 visit. If there is more than one value on or before Day 1, the value (scheduled or unscheduled) closest to and prior to (including on) the date of first dose will be used as the baseline value.

#### 5.4.2 Study Day Calculation for Reporting Purposes

The following conventions will be used to calculate study day for reporting purposes:

- Study Day = date of measurement – first dose date +1, if date of measurement is on or after the first dose date.
- Study Day = date of measurement – first dose date, if date of measurement is prior to the first dose date.
- Day 1 is the first dose date, no Day 0 is defined for this study.

#### 5.4.3 Visit Windows

Visit windows will not be derived for analyses and instead the nominal visit from the eCRF will be used. A last available assessment will be derived as the last value on treatment.

#### 5.4.4 Missing and Partial Data

Missing data may be imputed for some endpoints as seen in the following sections. For partial dates, the algorithms for imputation will vary depending upon the parameter, the details can be found in [Appendix A](#).

## 6 Subject Disposition

A summary of disposition of subjects will include the number and percentage of subjects for the following categories: subjects screened, subjects randomized, subjects treated (safety population), subjects in the ITT population, subjects in the PP population, subjects completed, and subjects discontinued from the study. All percentages will be based on the number of subjects randomized.

The reasons for study discontinuation will also be summarized in this table. The reason for discontinuation may include any of the following: adverse event, death, lost to follow-up, withdrawal of consent, or other. Only one reason for study discontinuation will be recorded. For subjects lost to follow-up, the number of days until lost to follow-up will also be presented using descriptive statistics. The number of days until lost to follow-up on study is defined as the number of days from randomization until the date of last contact.

## 16.1.9 Documentation of Statistical Methods

Receptos, Inc.  
Protocol RPC01-201

Statistical Analysis Plan – Part A, V1.2  
Date Issued: May 20, 2014

A listing will present data concerning subject disposition.

## 7 Demographics, Medical History and Baseline Characteristics

### 7.1 Demographics

The demographics and baseline characteristics will be presented in a table. The demographic characteristics consist of age, age category, sex, race, ethnicity, weight, weight category, height, body mass index, region, and stratification factors. A subject's age in years is calculated using the date of the informed consent and date of birth. Age will be summarized using the descriptive statistics. The number and percentage of patients in each age category (18-19, 20-29, 30-39, 40-49, 50-55, and >55, as well as <40, ≥40), and in each race category (White, Black, Asian, American Indian or Alaska Native, Native Hawaiian or Other Pacific Islander, and Other) will be reported. The summaries will be presented for both ITT and Per-Protocol populations.

### 7.2 Medical History

#### 7.2.1 General Medical History

Medical history data other than for MS will be presented in a table. The table summary will show the number and percentage of subjects with a significant history for each body system. Percentages will be calculated out of the number of subjects in the Safety population. Significant medical history including specific details will be listed in a listing.

#### 7.2.2 Multiple Sclerosis Disease History

The following multiple sclerosis disease history parameters will be summarized using the descriptive statistics

- EDSS score at baseline
- EDSS score category at baseline
- Age at MS symptoms onset
- Age at MS diagnosis
- Years since MS symptoms onset
- Years category since MS symptoms onset
- Years since MS diagnosis
- Years category since MS diagnosis
- Number of relapses within the last 12 months prior to screening
- Number of relapses within the last 24 months prior to screening
- Number of GdE lesions at baseline

The following duration categories will be used for the years since MS symptom onset and years since MS diagnosis: 0 - <1, 1 - <2, 2 - <5, 5 - <10, 10 - <15, >=15. EDSS score at baseline will be summarized at categories: 0 - 2, 2.5 - 3.5, 4 - 5, >5. Number of relapses within the past 12 and 24 months will also be summarized at categories: 1, 2 - 3, >=4.

## 16.1.9 Documentation of Statistical Methods

Receptos, Inc.  
Protocol RPC01-201

Statistical Analysis Plan – Part A, V1.2  
Date Issued: May 20, 2014

MS history data will be presented in a listing. Incomplete diagnosis dates will be imputed as detailed in [Appendix A](#).

### 7.3 Inclusion and Exclusion Criteria

The details of Inclusion and Exclusion criteria are listed in [Section 9.4.1](#) and [9.4.2](#) of the protocol.

The protocol deviations/violations will be presented in a listing.

## 8 Treatments and Medications

### 8.1 Prior and Concomitant Medications

All treatments being taken by the subjects on entry to the study or at any time during the study in addition to the investigational product are regarded as concomitant treatments and must be documented on the appropriate section of the eCRF. A history of all prior medications needs to be documented to at least 4 weeks prior to study participation, and a history of previous treatments for MS needs to be documented for the prior 2 years. All medications will be coded with the WHO Drug dictionary.

Prior and concomitant medications will be summarized by drug class and Preferred Name. At each level of summarization, a subject is counted once if he/she reports one or more medications at that level. Drug class will correspond to the ATC Level 2 term.

Prior medications are defined as medications with a stop date occurring before the first dose date. Concomitant medications are defined as medications with a start date or a stop date occurring on or after the first dose date. Medications with start and stop dates which bracket the first dose date will be summarized as both prior and concomitant medications.

Prior and concomitant medications will be presented in a listing.

### 8.2 Study Treatments

For all subjects in both Part A and Part B of the study, initial study treatment will consist of a 7-day dose titration regimen. For subjects randomized to receive active treatment with RPC1063 in Part A or Part B, this regimen will consist of RPC1063 0.25 mg starting on Day 1 for 4 days, then RPC1063 0.5 mg starting on Day 5 for 3 days, followed by the assigned treatment level beginning on Day 8.

#### 8.2.1 Extent of Exposure

Extent of exposure is defined as the total number of days a subject is exposed to any study drug. Because there is no medication diary, the extent of exposure is defined as the total number of days from the first dose date (Day 1) to the last dose date as recorded on

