9.1.1. Study Schematic and Schedule of Events

Figure 1 Study Schematic

CONFIDENTIAL

The information contained herein may not be used, disclosed, or published without the written consent of Receptos.

Table 1 Schedule of Assessments – Part A: Screening, Baseline, and Treatment Period Visits

Procedure	Screening	Baseline	Double-Blind Placebo-Controlled Period							
	Initial (-30 days)	D1 (W1)	D5 ¹ (W1)	D8 ¹ (W1)	D29 (W4) (±3d)	D57 (W8) (±3d)	D85 (W12) (±3d)	D113 (W16) (±3d)	D141 (W20) (±3d)	D169 (W24) ^{2,12} (±3d)
Informed consent	X									
Inclusion/exclusion criteria	X	X								
Medical history	X	X ³								
Clinical laboratory tests ⁴	X	X			X		X			X
Urine/serum pregnancy (women of childbearing potential only) ⁵	X	X			X	X	X	X	X	X
Coagulation panel	X									X
sTSH	X									X
Total Ig (IgA, IgG, IgM)										
Viral serology ⁶ , and syphilis RPR	X									
TB testing ⁷	X									
Complete physical examination	X									X
Height ⁸ and weight	X	X								X
Vital Signs	X	X ¹⁰	X ¹⁰		X	X	X	X	X	X ¹¹
Chest X-ray ⁹	X									
12-lead ECG	X	X ¹⁰	X ¹⁰		X		X			X ¹¹
Holter monitoring		X ¹⁰	X ¹⁰	X ¹⁰						
Enroll patient, contact IVRS	X									
Randomization		X								X ¹²
Study drug administration		X	X	X	X	X	X	X	X	X ¹²
Administer study drug at clinic		X	X	X			X			X ¹²
Dispense study drug and patient diary		X			X	X	X	X	X	X ¹²
Study drug accountability and compliance check					X	X	X	X	X	X
Brain MRI	X					X	X	X	X	X
EDSS and neurological examination	X						X			
MSFC and LCLA	X ¹³	X					X			

CONFIDENTIAL

The information contained herein may not be used, disclosed, or published without the written consent of Receptos.

Procedure	Screening	Baseline	Double-Blind Placebo-Controlled Period							
	Initial (-30 days)	D1 (W1)	D5 ¹ (W1)	D8 ¹ (W1)	D29 (W4) (±3d)	D57 (W8) (±3d)	D85 (W12) (±3d)	D113 (W16) (±3d)	D141 (W20) (±3d)	D169 (W24) ^{2,12} (±3d)
MSQOL-54		X								X
Pulmonary function tests ¹⁴	X						X			X
OCT ¹⁵	X									X
Dermatological (skin) examination	X									X
C-SSRS	X	X			X	X	X	X	X	X
Standard PK sampling ¹⁶		X			X		X			X
Plasma biomarkers										
Prior/Concomitant therapy										
AEs/SAEs ³	X	X	X	X	X	X	X	X	X	X

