9.5.9. Treatment Compliance

It is the Investigator's responsibility to ensure that patients are correctly instructed on how to take their study medication and that each patient is fully compliant with their assigned dosage regimen. Records of study medication used and intervals between visits will be kept during the study. Drug accountability will be noted by the field monitor during site visits and at the completion of the study. Patients will be asked to return all unused medication at the end of the study. The study treatment should be dispensed by the Investigator, or by a qualified individual under the Investigator's supervision. An up-to-date treatment inventory/dispensing record must be maintained as described above in [Section 9.5.5.2](#).

Overall study non-compliance is defined as taking less than 80% or more than 120% of study medication during the entire treatment period.

Details unique to Parts A or B are described below.

Part A

At each visit, previously dispensed study medication capsules will be collected by the Investigator and compliance assessed. Patients will record capsules intake in a dosing diary that will be reviewed periodically by site staff and the Clinical Monitor. Patients exhibiting poor compliance as assessed by medication counts (i.e., 2 or more missed medication days in 1 week) and response to the question "Did you take your medication regularly?" should be counseled on the importance of good compliance to the study dosing regimen. Patients who are persistently non-compliant (< 80% or > 120%) should be discussed with the Medical Monitor to determine whether they should be withdrawn from the study.

Part B

Compliance with IFN β -1a dosing is to be monitored and recorded by site staff. Patients will record IFN β -1a treatment in a dosing diary that will be reviewed periodically by site staff and the Clinical Monitor.

Compliance with RPC1063 capsules will be assessed as described above for Part A.

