12.6. Clinical Laboratory Parameters and Abnormal Laboratory Test Results

Clinically significant changes, in the judgment of the Investigator, in laboratory parameters (abnormalities) will be recorded as AEs.

During the treatment period, all Total WBC and WBC differential results will be blinded. If any of the following results are observed, the Investigator will be notified and asked to repeat the laboratory tests:

- Absolute lymphocyte count [ALC] < 200 cells/ μ L
- Absolute neutrophil count [ANC] < 1000 cells/ μ L
- Total WBC > 20,000 cells/ μ L

If the repeat values also exceed these limits, the Investigator will be informed that the patient's results for the abnormal parameter have fallen outside the acceptable thresholds.

If ANC or total WBC counts are confirmed outside the acceptable limits, the Medical Monitor will contact the treating investigator to request close monitoring for risk of infection and appropriate follow-up, at the discretion of the investigator.

If ALC results are confirmed as below 200 cells/ μ L, the investigator will be instructed that study drug is to be temporarily discontinued. Laboratory testing will be repeated weekly until the results have returned to within the following acceptable ranges:

- ALC > 500 cells/ μ L

When values have returned to acceptable values, the Investigator will be informed that the values are no longer outside of the acceptable range and that study drug may be restarted. (See [Section 9.5.1](#) instructions on resuming treatment after dose interruptions.)

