#### 8.2.2 Treatment Compliance

Study drug compliance will be calculated for each subject by taking into account whether a subject takes all doses of study drug as instructed. The study drug compliance rate will be summarized by treatment group using descriptive statistics for the Safety Population. The overall study drug compliance rate will be calculated by dividing the total number of capsules taken at all visits by the total number of capsules prescribed for all visits based upon the duration in the study and then multiplying by 100. The number and percentage of subjects in each compliance rate category (<=50%, 51-60%, 61-70%, 71-80%, and 81-100%, >100%, <80%, and >120%) will be reported. Percentages will be calculated out of the number of subjects who have been dosed in the study period.

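### SAP 8.2.1 counts interruption days as exposure because it says no diary exists, which the protocol contradicts; separately, SAP 8.2.2 is silent on how protocol-directed holds enter compliance

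*SAP*

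**What the plan says.** **Exposure.** SAP 8.2.1 opens with a concept: "Extent of exposure is defined as the total number of days a subject is exposed to any study drug". It then replaces the concept with a calendar rule: "Because there is no medication diary, the extent of exposure is defined as the total number of days" from Day 1 to the last dose date on the end-of-study page. It also promises a summary of a second measure, study drug exposure, which the SAP text does not define.

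**Diary.** Protocol 9.5.9, under Part A, says: "Patients will record capsules intake in a dosing diary that will be reviewed periodically by site staff and the Clinical Monitor". Table 1 has a row "Dispense study drug and patient diary", marked at Day 1 and at each four-weekly visit from Week 4. The introduction to protocol Section 10 has patients write dosing times in the diary when a postdose PK sample is due.

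**Holds.** Under protocol 12.6, if an absolute lymphocyte count below 200 cells/µL is confirmed, "the investigator will be instructed that study drug is to be temporarily discontinued". Testing is then weekly until the count exceeds 500, after which drug may be restarted. No maximum length is given.

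**Compliance and the per-protocol (PP) set.** SAP 8.2.2 divides capsules taken by "the total number of capsules prescribed for all visits based upon the duration in the study". SAP 5.3.2 excludes patients from PP for this reason: "Poor study drug compliance: compliance up to last dose of study drug <80" per cent.

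**The concern.** There are two separate problems.

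1. The only reason SAP 8.2.1 gives for the first-to-last-dose rule conflicts with the protocol. The rule also departs from the section's own concept of exposure, because days off drug between two dosing periods are counted as days on drug.
2. SAP 8.2.2 does not say whether doses withheld on protocol instruction count as prescribed. If they do, a patient who obeyed the protocol can be classed as a major deviator for poor compliance and dropped from PP.

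Both would act unevenly across arms. A low-lymphocyte hold follows from the drug's pharmacodynamic effect, so it should occur mainly on RPC1063. Exposure would be overstated, and compliance understated, chiefly in the active arms of a placebo-controlled comparison.

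**Working it through.** The plan states no figure on this point, so there is none to reproduce.

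**Inputs**
- Treatment period: 24 weeks = 168 days (the Week 24 visit is Day 169, Table 1).
- Capsules (protocol Table 6): one a day, except two a day on Days 5 to 7. Planned total = 168 + 3 = 171.
- Holds are placed after Day 8, so each held day is one capsule.
- PP limit: below 80% (SAP 5.3.2).
- Hold lengths are assumptions; the documents give none.

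**Exposure, hold of h days followed by a restart**

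SAP exposure = 168. True exposure = 168 − h. Overstatement = h / (168 − h).

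**Compliance, if held doses stay in the denominator**

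Compliance = (171 − h) / 171.

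| Hold (days) | Days dosed | Overstatement of exposure | Compliance |
|---|---|---|---|
| 7 | 161 | 4.3% | 95.9% |
| 14 | 154 | 9.1% | 91.8% |
| 28 | 140 | 20.0% | 83.6% |
| 34 | 134 | 25.4% | 80.1% |
| 35 | 133 | 26.3% | 79.5% |

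The PP threshold is therefore 35 held days: 136/171 = 79.5% is out, while 137/171 = 80.1% stays in. Counting days instead of capsules would suggest 34 (134/168 = 79.8%), but SAP 8.2.2 counts capsules.

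**Shorter holds that suffice**
- Assumed adherence *a* outside the hold, with compliance = a(171 − h)/171:
  - 95%: 28 days (0.95 × 143/171 = 79.4%)
  - 90%: 20 days (0.90 × 151/171 = 79.5%)
  - 85%: 11 days (0.85 × 160/171 = 79.5%)
- Last dose at Day 84 (87 capsules): 18 days (69/87 = 79.3%). Last dose at Day 56 (59 capsules): 12 days (47/59 = 79.7%).

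**Holds never followed by a restart.** Exposure stops at the last dose, so nothing is overstated. On the time base of SAP 5.3.2, which ends at the last dose, compliance is not lowered either. SAP 8.2.2 uses duration in the study, which could run longer. For example, with a last dose at Day 84 and 28 further days in the study, it could be read as 87/(87 + 28) = 75.7%. The two sections should not allow different answers for the same patient.

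**With hold days removed from both measures.** The 35-day patient has 133 exposure days and 100% compliance, and stays in PP.

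**Are such holds plausible?** Entry allows a lymphocyte count of 800/µL (exclusion 35). The 1 mg dose targets a decrease of about 70% (protocol 9.2), and Phase 1 showed 71.1% at 1 mg (7.2.4). At the entry floor this leaves 800 × 0.30 = 240 or 800 × 0.289 = 231/µL, against a trigger of 200. This shows only that the trigger is within reach on active drug. It gives no frequency.

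**The case against.** Several points on the other side are sound.

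- **The diary sentence may not be simply wrong.** SAP V1.2 is dated 20 May 2014 and protocol V4.0 is dated 1 October 2014. The SAP describes a 24-week extension where V4.0 has at least 48 weeks, so it appears to follow an earlier protocol. Protocol 9.5.9 has the diary reviewed by site staff and the monitor, without saying that entries reach the database. The SAP may mean that no diary data are available for analysis. The texts still conflict and need reconciling.
- **The PP consequence does not come from the diary sentence.** A reader might infer that denying the diary is what costs patients their PP place. It is not: compliance rests on capsule counts, and correcting 8.2.1 alone would leave 8.2.2 and 5.3.2 unchanged.
- **A hold does not by itself exclude anyone.** It must bring compliance below 80%, which takes five weeks in an otherwise fully adherent 24-week patient.
- **The adverse reading of 8.2.2 is not certain.** The section speaks of doses taken as instructed, which could exempt withheld doses. The PP criteria are also to be finalised in a blinded review before database lock, which could settle such cases. Neither is a written rule.
- **Few patients may be affected.** Scheduled on-treatment haematology in the 24 weeks falls at Weeks 4, 12 and 24, so scheduled testing can start a hold with a restart inside the period at only two visits. The mean decrease also leaves counts above 200 even at the entry floor.
- **Little depends on it.** ITT is primary (SAP 9). AE tables are patient-count incidences (10.1.1), and the relapse rate uses days in the study (9.2.1).

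**Conclusion.** The point holds as a minor correction with two independent parts.

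1. SAP 8.2.1 conflicts with the protocol on the diary and counts interruptions followed by a restart as exposure. The overstatement is 20% for a 28-day hold and 26% for a 35-day hold over 168 days.
2. SAP 8.2.2 leaves protocol-directed holds unaddressed. Read literally, at least 35 held days exclude an otherwise fully adherent 24-week patient from PP, and fewer do so with other missed doses or an early last dose.

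This rests on the Table 6 capsule schedule, holds placed after Day 8, and held doses being counted as prescribed. That such holds fall mainly on RPC1063 is an expectation from the drug's mechanism. Their number and length are not given.

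A reader might go further and infer that the PP analysis will be biased by loss of RPC1063 patients, or that the primary result is at risk. The documents support neither: no hold frequency is available, the blinded review may exempt such patients, and the primary analysis is in the ITT population. The effect is confined to the exposure and compliance tables and the supportive PP analysis.

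**What to change.** - **SAP 8.2.1:** reconcile the diary statement with protocol 9.5.9, Table 1 and Section 10. If the meaning is that diary entries are not in the database, say so.
- **Exposure:** report days actually dosed, derived from diary, accountability or interruption records, beside the first-to-last-dose duration. Define study drug exposure.
- **SAP 8.2.2 and 5.3.2:** remove protocol-directed hold days from the compliance denominator before applying the 80% rule, and use the same time base, up to last dose, in both sections.

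The cost is SAP wording and one derivation, mostly from records the protocol already requires. The downside is that hold or diary dates must be in the analysis data set; whether they are collected there cannot be seen from the two documents.
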